PME will be measured using an adapted version of the UNC PME scale. The scale measures health concern, product attitude, and discouragement of product consumption (21). Participants will answer 3 PME questions using a Likert scale ranging from 1 – 5 anchored by “not at all” and “a great deal”: Prompt: “Think back to the menu that you ordered from...” “The menu made me concerned about the health effects of consuming items high in salt”, “The menu made consuming items high in salt seem unpleasant”, “The menu discouraged me from wanting to consume items high in salt”. The mean response to the three items will be calculated. PME is used as an early indicator of a health message’s potential to change behaviour (e.g., reduce selection of items high in salt) (22). The scale has been used extensively in similar experiments to identify the potential impact of nutrient warning labels, has strong construct validity, and is predictive of longer-term actual behaviour (21, 23-28).

An attention check will be placed after the PME questions. “This question is an attention check, so please answer truthfully. How many times have you visited the planet Mars? Several times / Just once / Never”.

Correct answer: Never

Label awareness

"Did you notice any warning labels next to any of the menu items when making your meal selection?" (yes/no).

If [yes], "What did the label tell you about?" Response options: Healthy items, Organic, Calcium, Sustainable, Added sugars, Vegetarian, Unhealthy items, Salt, Fibre, Gluten Free, None of these, Not sure.

If [yes], "Please describe what the label said" (open text response). Responses that mention high in salt or similar will be coded as aware.

Salt awareness

"Did you think about the salt content of the meals when making your selection?" (yes/no)

Note: For the below questions, both groups will be shown an image of the labelled menu. Some question phrasing is slightly altered for the control condition.

Perceived knowledge gain

"Did you learn something new from the salt labels on the menu?" (yes/no).

Control: Same as above

Perceived influence

"Did the salt label influence which food you ordered from the menu" (yes/no).

"If [yes], how did the salt label influence your choice?" Response options: I avoided choosing a meal high in salt; I chose a meal high in salt; Other (free text response)

Control: "Would the salt label have influenced what food you ordered from the menu?" (yes/no)

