Participants will receive a link to a dietary recall questionnaire (Intake24, <https://intake24.co.uk/>) via email the next morning after taking part in the study, which they will be prompted to complete before midnight that day. They will be asked to provide as much detail as possible on what they had for dinner, snacks, and drinks after the restaurant visit. Based on this information and salt values calculated by Intake24, we will estimate the total salt consumed by the participants for the rest of the day after the visit.

Other macronutrient intake

Total kcal, sugar, and saturated fat intake [i.e., other nutrients that are not the main warning focus] will be calculated based on the nutritional content of the order of the participant.

Additional measures

Food choice motives

The “health” subsection of the Food Choice Questionnaire (29) will be used to measure the extent to which health motives may influence participants’ food choices. The subsection consists of 6 items, e.g. “It is important to me that the food I eat on a typical day....is nutritious” answered on a 4-point Likert scale ranging from “Not at all important” to “Very important”. We will calculate the mean response for the six items.

Aim guessing

Participants are told that the study is about dining habits in restaurants. At the start of the post-meal assessments, participants will be asked what they think the aims of the study were (free text response). Any participant that guesses the study aims to be investigating the influence of food warning labels on food choice will be coded as being aware of study aims. One researcher will code awareness of aims ([name]) and a second researcher will independently verify the coding.

Study flow

Recruitment	
 - Participants will be recruited via online adverts, word of mouth, and an existing participant database maintained by researchers at the University of Liverpool. - A link to the screening questionnaire will be provided. (Appendix A) - Participants will be stratified by SEP, age, and sex. 				

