
 - Participants will receive a standard menu without nutrient warning labels. 	
 - Participants will receive a menu featuring a nutrient warning label next to items high in salt. Text at the bottom of the menu will read “[label image] indicates that the salt content of this item is higher than 50% of the daily recommended limit (6g per day). High salt 				

		intake can increase blood pressure and risk of heart disease and stroke.”
	
 - The participants will be asked to order lunch from the menu and a drink (optional) and write this down on an order form (Appendix D) - A researcher will communicate the order with the kitchen, take a photo of the meal when it is ready to be served and take a second photo when the participant is finished with the meal. The researcher will send themselves each photo on WhatsApp labelled with the participant ID. 	
Post-meal assessments (Qualtrics) (Appendix E)	
 - After finishing their meal, participants will be provided with an iPad. They will answer a question about what they think the aim of the study was in an open-ended response format. - Next, participants will complete measures of PME, label awareness, salt awareness, perceived knowledge gain, perceived influence, and policy support. - Finally, participants will answer questions on demographic characteristics (including frequency of eating OOH) and health motives. 	
Later intake	
 - After the restaurant visit (same day), participants will receive a link to an online questionnaire assessing their dietary intake for the rest of the day after the restaurant visit, to be completed before they go to bed (Intake24). - This will enable us to calculate salt consumed post intervention for the rest of that day. - They will also be requested to answer some additional questions on demographic characteristics. 	
Additional demographic questions (Appendix F) and debriefing (Appendix G) (Qualtrics)	
 - After completing the dietary intake questionnaire, participants will be asked to answer some additional questions on demographic characteristics. - Upon completion, participants will be debriefed on study aims. 	

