A logistic regression will be performed to assess the odds of selecting a high salt meal in the labelled menu group, using the control menu group as the reference category. The same covariates as above will be included.

As some participants are likely to bring guests to the restaurant and guest tables are the unit of randomization, there may be clustering for outcome variables (i.e., the variation in PME and/or salt purchase/intake may be partially explained by table). We will test for clustering effects by comparing the within-table variability for outcome variables to the between-table variability. We will use the likelihood ratio test to ascertain the difference in likelihoods between the two. If this is statistically significant ($p < .05$) then there is enough evidence to suggest that there is a clustering effect of table groups eating together. If there is evidence of clustering then we will perform a series of linear mixed model analyses, with label condition as an independent variable, and table group as a random effect for primary and secondary outcomes.

Exploratory analyses

Linear regressions will be performed to assess differences in menu conditions in terms of later salt intake, and intake of other macronutrients. This is to examine whether individuals engage in any compensatory eating behaviour after seeing the labels (e.g., they are aware that they consumed a

high salt meal and therefore reduce their salt intake later in the day), or whether intake of other macronutrients (e.g., calories) is impacted. Again, the same covariates as above will be included.

Sensitivity

Sensitivity analyses will be conducted to test if results are the same after removing any participants that correctly guess the aims of the study (i.e., the effect of salt warning labels on food choice, or similar). If many participants identify the study aims (e.g., > 25%) we will examine if study aim awareness status moderates any effects of labelling by including this as a covariate (categorical) in analyses. Any deviations in findings from the main analyses will be reported.

Missing data

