We do not foresee missing data being a problem as when we design measures in Qualtrics all fields will require a response, and all data will be collected by a researcher during the restaurant visit. However, it is possible that some participants will not complete the online questionnaire to assess later intake after the restaurant visit. Any missing data for later nutrient intake will be imputed.

Multiple comparisons

The alpha will be set at .05 for primary and secondary outcome analyses. To adjust for multiple comparisons, the alpha for exploratory analyses alpha will be reduced to .01.

Sample size

The label in the present study (or a similar label) has not previously been tested in a real-world UK context, in terms of PME or food choice. A RCT examining the effects of 'high in' added sugar labels on PME found large effects ($d = 0.58 - 0.63$) (7). A meta-analysis on food labelling found a small effect ($OR = 0.65$, or $d = .24$) of warning labels in terms of reducing consumers' probability of selecting less healthy items (31). However, a RCT examining the effects of 'high in' sodium labels on salt (g) and 'high in' item choice found very small effects ($d = 0.03$ and 0.04 respectively) (9), but there are important methodological differences (e.g., menu size) between this study and the present study. The primary purpose of the present study is to examine PME, so we will therefore power the study for this primary outcome, but in doing so we will have reasonable power to detect small-medium effects for our secondary outcome (food choice).

In the present study, G power calculation indicates a minimum sample of 260 participants (130 per condition) will provide sufficient power (80%, two-tailed) to detect small-medium between condition effects ($d = 0.35$) of the salt warning label on PME, salt purchased, and salt intake using between-subject ANOVAs (as planned).

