Start of Block: Additional assessments

Display This Question:

If Please select the letter which is circled on your sticker label. If you are unsure, please ask th... = B

Here is the menu you ordered from. The menu features salt warning labels next to items that exceed 50% of the daily recommended limit for salt intake: [menu B image]

Display This Question:

If Please select the letter which is circled on your sticker label. If you are unsure, please ask th... = A

Here is a slightly different version of the menu you ordered from. The menu features salt warning labels next to items that exceed 50% of the daily recommended limit for salt intake: [menu B image]

Did you learn something new from the salt labels on the menu?

Yes (1)

No (2)

Display This Question:

If Please select the letter which is circled on your sticker label. If you are unsure, please ask th... = B

Did the salt labels influence which food you ordered from the menu?

Yes (1)

No (2)

Display This Question:

If Did the salt labels influence which food you ordered from the menu? = Yes

How did the salt label influence your choice?

I avoided choosing a meal high in salt (1)

I chose a meal high in salt (2)

Other (please describe) (3) _____

Display This Question:

If Please select the letter which is circled on your sticker label. If you are unsure, please ask th... = A

Would the salt labels have influenced which food you ordered from the menu?

Yes (1)

No (2)

Display This Question:

If Would the salt labels have influenced which food you ordered from the menu? = Yes

How would the salt labels have influenced your choice?

- I would have avoided choosing a meal high in salt (1)
- I would have chosen a meal high in salt (2)
- Other (please describe) (3) _____

If the UK Government introduced policy requiring restaurant menu items high in salt to feature these labels, how would you feel?

- Strongly oppose (1)
- Oppose (3)
- Neutral (4)
- Support (5)
- Strongly support (6)

Please use this box to add any additional thoughts which you may have about the salt label.

End of Block: Additional assessments

Start of Block: Demographics

What is your age (in years)?

What is your sex? A question about gender identity will follow.

- Male (1)
- Female (2)

Which of the following best describes your gender?

- Man (1)
- Non-binary (2)
- Woman (3)
- Prefer to self-describe (4) _____
- Prefer not to say (5)

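### Controls see the labelled menu before the later-intake window opens, so the exploratory later-salt comparison has no unlabelled control and a null cannot rule out awareness-driven compensation

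*Combined protocol and SAP*

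**What the plan says.** **Exposure of controls.** The note before Perceived knowledge gain (Measures, Primary outcomes) says that for the items that follow "both groups will be shown an image of the labelled menu". Appendix E, Additional assessments, implements this. Diners with sticker letter A (the control menu) read "Here is a slightly different version of the menu you ordered from" and then "The menu features salt warning labels next to items that exceed 50% of the daily recommended limit for salt intake", with the Menu B image. The footnote on Menu B (Figure 4) links high salt intake to blood pressure, heart disease and stroke. Diners with letter B are shown the same image again.

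**Timing.** The Study flow table places this in the post-meal step: "After finishing their meal, participants will be provided with an iPad". The Later intake row comes after it. Under Missing data, the Qualtrics forms are set so that "all fields will require a response"; no control is planned to skip the block.

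**Outcome and analysis.** For Later salt intake the plan states that "we will estimate the total salt consumed by the participants for the rest of the day after the visit". Under Exploratory analyses, "Linear regressions will be performed to assess differences in menu conditions in terms of later salt intake". The purpose given there is: "This is to examine whether individuals engage in any compensatory eating behaviour after seeing the labels". The example offered is a diner who knows that lunch was salty and cuts salt later that day. Exploratory analyses are tested at alpha .01 (Multiple comparisons).

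**The concern.** The analysis compares randomised arms to learn what happens after people see the labels. That needs one arm that has not seen them when the outcome is generated. Here the control arm sees them at the restaurant, together with the statement that lets each diner work out whether the dish just eaten was high in salt. This is the information that the plan's example relies on to trigger compensation.

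At stake is the interpretation of one exploratory result. If the two arms report similar later salt, the natural reading under the current text is that labels do not provoke compensation. The data could not separate that from both arms compensating to a similar degree. The plan holds back the debrief until after the dietary recall, but no section acknowledges, avoids or adjusts for showing controls the labelled menu beforehand.

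**Working it through.** **1. Order of events for a control diner** (Study flow; Appendix E)

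1. Orders from Menu A and eats.
2. Answers the aim-guessing, sharing, condiment, PME, label-awareness and salt-awareness items.
3. Sees Menu B and the half-of-daily-limit statement, and is asked whether the labels would have changed the order.
4. Leaves. The later-salt window starts.
5. Completes Intake24.

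Step 3 precedes step 4 for all controls. The recall is sent the next morning according to Procedure and Later salt intake, but the same day, for completion before bed, according to Study flow. The intake window follows the questionnaire either way.

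**2. What the arms contrast**

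- Labelled arm: label at ordering, then again after the meal.
- Control arm: label after the meal only.
- The arms may also differ in what was eaten at lunch, which is the intended effect of the label.

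**3. Effect on the awareness route**

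Let p1 and p0 be the proportions eating a high-salt dish in the labelled and control arms. Let k be the cut in later salt among labelled-arm diners who know they ate one, and r the control response as a share of k. The documents give none of these values.

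- Against a control never shown the label: difference = −k·p1.
- As planned: difference = −k·p1 + r·k·p0 = −k(p1 − r·p0).
- Ratio of planned to unlabelled-control contrast = 1 − r·p0/p1.

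If the arms ate similar meals (p1 = p0), the ratio is 1 − r: 75%, 50%, 25% and 0% at r = 0.25, 0.5, 0.75 and 1. If labels steer diners away from salty dishes (p1 < p0), the ratio is smaller, and the sign reverses once r exceeds p1/p0. The direction is therefore not fixed.

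**4. Illustration in terms of power**

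The plan's own figure first. For d = 0.35, 80% power and two-sided alpha .05, n per arm = 2(1.960 + 0.842)²/0.35² = 128.2, rounded up to 129. The t-test solution is 129.1, rounded up to 130 per arm, so the stated 260 is reproduced. It was set for PME, salt purchased and salt intake, and does not bear on this point except to give the arm sizes.

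For later salt, assume a true effect of d = 0.35 (the documents give none), similar meals, two-sided alpha .01, and no allowance for table clustering or covariates. Power ≈ Φ(0.35(1 − r)√(n/2) − 2.576). For example, with n = 130 and r = 0.5: 0.175 × 8.062 − 2.576 = −1.165, giving 12.2%.

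| r | 130 per arm | 250 per arm |
|---|---|---|
| 0 | 59.7% | 90.9% |
| 0.25 | 32.3% | 64.0% |
| 0.5 | 12.2% | 26.8% |
| 0.75 | 3.1% | 5.5% |
| 1 | 1% | 1% |

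The 250 per arm assumes an equal split of the stated maximum of about 500. At r = 1 the rejection rate is simply alpha. The table restates the assumed r; it is not an estimate of the loss.

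**5. Outcomes not touched**

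PME, label awareness and salt awareness are answered before the image appears. Salt purchased, labelled item selected, salt eaten at the meal and the order-based nutrient totals are fixed by then.

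**The case against.** The strongest reply is that the damage is narrow. Later salt sits under Secondary outcomes in Measures, but it is analysed as exploratory at alpha .01, is not named in the objectives, and belongs to a study that calls itself a pilot. That stands, and it limits the severity.

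Four stronger readings are tempting, and the documents do not support them.

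- *The comparison cannot test compensation at all.* A lunch changed by the label may itself alter later intake, and that route is still a randomised comparison. Only the awareness route loses its unlabelled control.
- *The arms differ only in when they saw the label.* Appendix E shows Menu B again to the labelled arm, so those diners see it twice, and the meals may differ as well.
- *The result is biased towards zero.* That holds for similar meals. The planned regression does not condition on the meal, and a shift in meal choice could reverse the sign.
- *The plan relies on this analysis to judge whether a salt reduction at lunch is made up later.* No section says so. The only salt example runs the other way: less salt later, after a salty lunch.

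It is also fair to object that relocating the menu image has a real price. Perceived knowledge gain and perceived influence are primary objectives, and at the table they are forced-response items. Missing data expects some people not to complete the later-intake questionnaire, and plans imputation only for later nutrient intake. That stands too, and it is why rewording is the main remedy.

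**Conclusion.** The point holds for the exploratory later-salt analysis and goes no further. As planned, it compares label at ordering plus afterwards with label afterwards only. It cannot isolate compensation that comes from becoming aware of a high-salt meal, and a null is uninformative on that question.

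The size is unknown, because it depends on r and on any shift in meal choice, and the documents quantify neither for this outcome. With similar meals the awareness effect shrinks by the factor 1 − r; with a shift in meal choice it may reverse. A reader might infer that the trial's main conclusions are compromised. They are not, because PME, label and salt awareness, and the lunch salt outcomes are settled before controls see the labels. Severity: should be fixed.

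**What to change.** **Recommended.** Amend Exploratory analyses to say that the later-salt comparison contrasts label exposure at ordering plus after the meal with exposure after the meal only, and that a null will not be taken as evidence that people do not compensate after seeing the labels. The change is to wording only. The cost is a weaker exploratory claim.

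**Optional, if the sponsor wants a label versus no-label test.** Move the block that uses the Menu B image, for both arms, to the Qualtrics form that already follows Intake24 (Appendix F). This has two costs. Perceived knowledge gain and perceived influence (primary objectives) and policy support (a secondary objective) would become open to non-completion and later recall. Controls would also still be primed about salt by the PME and salt-awareness items answered at the table, so the comparison would be cleaner but not free of salt cues.

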To date, the impact of nutrient warning labels has not been tested in a real-world randomised controlled trial (i.e., in a restaurant), or in a UK context. Recent work suggests that UK consumers support the introduction of nutrient warning labels, and their PME was rated as significantly higher relative to a control label (QR code) (13). This study aims to test the effect of a menu featuring salt warning labels (design informed by previous work (13)) on perceived message effectiveness relative to a menu with no labels in a real-world restaurant environment. The study will also act as a pilot experiment for examining the impact of the salt warning label on food choice and subsequent salt intake in real-world conditions.

Primary objectives:

- To measure the PME of a menu featuring salt warning labels relative to a menu with no labels
- To measure label awareness, perceived knowledge gain, and perceived influence of the label on food choice

Secondary objectives:

- To identify whether there is an effect of the salt warning label on:
 - Food choice (label/no label)
 - Total salt selected
 - Total salt intake
- To examine support for the introduction of a salt warning label policy in the UK

Experimental design

The study will be a between-subjects randomised controlled trial design. The between-subject factor is the menu labelling. In the experimental condition, a nutrient warning label will be placed next to menu items that are high in salt. In the control condition, there will be no labels. The outcome will be (i) perceived message effectiveness, (ii) salt selected, label (y/n) selected, and salt intake. This will allow us to examine whether the salt warning label intervention impacts perceived message effectiveness and food choice relative to the control condition.

Participants and recruitment

Recruitment

Participants will be recruited via social media adverts (Facebook, Instagram), a database maintained by researchers at the University of Liverpool, and word of mouth. Interested participants will be asked to click a link which will take them to an online screening questionnaire (Appendix A). Participants can bring a maximum of nine guests to the restaurant. Guests will be pre-screened in advance to ensure eligibility. In pre-study instructions participants will be informed that any guests they bring will participate in the study.

Sampling

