Our service and kitchen staff handle a wide range of ingredients including nuts, dairy and ingredients containing gluten. Please inform your server of any food allergies or intolerances prior to ordering your food.

THE BALTIC HOTEL [name] thebaltichotelliverpool.com

Figure 4: Menu (B) for the experimental condition

ME NU

EVERYDAY FROM 11.30AM

Light Bites/Small Plates

Mushroom Soup served with crusty bread and butter	£5.50
Cajun Chicken Flatbread Flatbread filled with Cajun Chicken, roasted pepper, herb salad & lime mayonnaise	£7.95
Beetroot Hummus Flatbread Flatbread served with Hummus, house salad & pomegranate dressing	£6.95
Ruban Toasted sandwich Sliced pastrami, Baltic pickles, Sauerkraut with melted Gruyere	£8.95
Mexican Cheese on toast A blend of melted cheese, chillies and spring onion.	£5.95
Loaded Dirty Fries Melted cheese, Baltic chilli and BBQ sauce - Add Chicken or Halloumi for £1.50	£5.95
Loaded Dirty Fries with chicken Melted cheese, Baltic chilli and BBQ sauce - Add Chicken or Halloumi for £1.50	£7.45
Loaded Dirty Fries with halloumi HIGH IN SALT Melted cheese, Baltic chilli and BBQ sauce - Add Chicken or Halloumi for £1.50	£7.45

Mains

Chefs Homemade Scouse HIGH IN SALT	£8.50
Served with crusty bread, pickled cabbage and beetroot	
Steak & Ale Pie HIGH IN SALT	£11.50
Served with house fries and mushy peas	
Baltic Black & White Burger	£10.00
HIGH IN SALT	
Black Burger Bun, Grilled Halloumi, peppers, tomato, lettuce, chilli BBQ relish served with house fries	
6oz Baltic Cheese Burger HIGH IN SALT	£10.95
A 6oz burger patty, Brioche bun, lettuce, tomato served with burger relish & House fries	
Steak & Eggs Hash Grilled 4oz Ribeye steak, creamy peppered hash potatoes topped with fried egg	£11.50
Super Food Salad Baltic house salad, quinoa, pomegranate, tenderstem Broccoli, cucumber, tomato, red onion served with Soy honey dressing Add Chicken or Halloumi for £1.50	£7.95
Super Food Salad with chicken Baltic house salad, chicken, quinoa, pomegranate, tenderstem Broccoli, cucumber, tomato, red onion served with Soy honey dressing	£9.45
Super Food Salad with halloumi Baltic house salad, halloumi, quinoa, pomegranate, tenderstem Broccoli, cucumber, tomato, red onion served with Soy honey dressing	£9.45

HIGH IN SALT indicates that the salt content of this item is higher than 50% of the daily recommended limit (6g per day). High salt intake can increase blood pressure and risk of heart disease and stroke.

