If [yes], how would the salt label have influenced your choice? Response options: I would have avoided choosing a meal high in salt; I would have chosen a meal high in salt; Other (free text response)

Policy support

If the UK Government introduced policy requiring restaurant menu items high in salt to feature these labels, how would you feel?" Likert scale ranging from 1 – 5 anchored by "strongly oppose" and "strongly support".

Control: Same as above

Additional thoughts on label

"Please use this box to add any additional thoughts which you may have about the salt label" (open text response).

Control: Same as above

Secondary outcomes

Total salt purchased

Determined based on the total order of the participant, including food and drink. Prior to study commencement, all menu items will be sent for nutritional analysis to determine salt content/100g. Menu items will be weighed before being sent for analysis using kitchen scales (Vitafit VT706), so that specific salt content per serving can be calculated.

Labelled item selected

Determined based on whether the food item selected featured a high in salt warning label (yes = 1, no = 0).

Total salt consumed

Salt consumption will be determined from the order that the researcher takes and an estimation of the proportion of the meal that was consumed. The researcher will take a photograph before and after consumption and will estimate the percentage consumed component(s) of the meal, taking into account whether participants leave a proportion of all meal components or specific components (e.g., low salt or high salt components). Participants will also be asked whether they shared any of their meal with someone else. A random 10% selection of percentage estimates will be performed by a second researcher to measure reliability. Food consumption will then be calculated by subtracting an estimation of the proportion of the meal that was consumed (taking into account if any has been shared) from the food purchase.

Later salt intake

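### The food-choice outcome is scored by a label that only Menu B carries, which conflicts with the planned high-salt comparison and scores one high-salt dish as 0 when it is ordered through an add-on

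*Combined protocol and SAP*

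**What the plan says.** - **Scoring rule** (Measures, Secondary outcomes, Labelled item selected): "Determined based on whether the food item selected featured a high in salt warning label", coded 1 for yes and 0 for no. This is the only operational definition of the outcome. It has no separate rule for controls, add-ons or orders of more than one dish.
- **Objective** (Secondary objectives): "Food choice (label/no label").
- **Control menu** (Experimental design): "In the control condition, there will be no labels". Figure 3 (Menu A) agrees.
- **Analysis** (Statistical analysis, Secondary): a logistic regression to "assess the odds of selecting a high salt meal in the labelled menu group, using the control menu group as the reference category". The interim text under Sample size uses the same high-salt-meal outcome, with PME, to decide whether recruitment continues.
- **Threshold** (Intervention): labels go on items above 3 g salt, half the daily limit. Five of the 16 dishes qualify.
- **Menu B** (Figure 4): the labelled line begins "Loaded Dirty Fries with halloumi HIGH IN SALT Melted cheese" and costs £7.45. Two entries above it, unlabelled and at £5.95, is "Loaded Dirty Fries Melted cheese, Baltic chilli and BBQ sauce - Add Chicken or Halloumi for £1.50". Menu A carries the same fries lines and add-on text.

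**The concern.** An outcome compared between arms must be able to take either value in both arms. This one is tied to a feature that exists in one arm only, while the model and the interim look treat it as a property of the dish. An analyst who follows the definition cannot fit the planned model, and one who follows the analysis section has to supply a definition that the protocol does not state.

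The menu adds a second gap. One of the five labelled dishes can be bought from an unlabelled line. Such an order contains a dish above the labelling threshold, yet the item selected carried no label, so the rule scores it 0. The outcome is a listed secondary outcome and one of the two that steer the interim decision, so its coding should be fixed before orders are seen.

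**Working it through.** **1. The plan's own figures.** For d = 0.35, 80% power and two-sided alpha 0.05, the normal approximation gives n per arm = 2 × (1.960 + 0.842)² / 0.35² = 128.1, rounded up to 129. The t-test solution is 129.1, so 130 per arm, as stated. The protocol's conversion of OR 0.65 also reproduces: d = |ln 0.65| × √3/π = 0.24. The 130 per arm is used below. Clustering by table is ignored.

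**2. The scoring rule applied literally.** Controls score 0/130 by construction. With x events in the labelled arm, the odds ratio is [x/(130 − x)] / [0/130], which is undefined. An illustrative unadjusted logistic fit did not converge (coefficient about 24, standard error about 17,700). With x = 6, Fisher's exact test gives p = 0.029, in the direction of labels increasing high-salt choice.

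**3. The add-on route.** £5.95 + £1.50 = £7.45, the price of the labelled line, for the same base dish with the same addition. It affects 1 of 5 labelled dishes. Orders are written by participants on a form with a free meal column (Appendix D), and no coding rule covers add-ons.

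**4. Possible size of an add-on effect.** The documents give neither a high-salt selection rate nor an add-on rate, so every rate here is assumed. Suppose 52 of 130 (40%) order a labelled dish in each arm, with no true effect. Suppose also that add-on orders score 0 in the labelled arm only:

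- 5 such orders: (47/83) / (52/78) = 0.566 / 0.667 = 0.85
- 2 such orders: (50/80) / (52/78) = 0.625 / 0.667 = 0.94

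More generally, let p0 be the true rate in both arms and m the share of labelled-arm orders lost. Then p1 = p0 − m and OR = [p1/(1 − p1)] / [p0/(1 − p0)]:

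| m | OR, p0 = 31% (5/16) | OR, p0 = 50% |
|---|---|---|
| 1% | 0.95 | 0.96 |
| 2% | 0.91 | 0.92 |
| 5% | 0.78 | 0.82 |

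**5. The same calculation with equal use.** Menu A offers the same add-on. If 5 diners in each arm use it and the ordered line is scored the same way in both, each arm has 47/130 and the odds ratio is 1.00.

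**6. Against the interim threshold.** On the d scale, OR 0.85 is |ln 0.85| × √3/π = 0.09 and OR 0.94 is about 0.04. The interim threshold of d = 0.25 corresponds to an odds ratio of 0.64.

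**The case against.** The strongest reply is that this is loose wording with an obvious meaning. The analysis and interim sections give the outcome an arm-neutral name. High in salt has a stated threshold, the five dishes are identifiable from Menu B, and both menus list the same dishes. Every item is analysed per serving before the study, and each meal is written down and photographed. A control order can therefore be matched to the five dishes, and halloumi fries can be recognised whichever line was used.

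Much of that stands. A reader might infer that the trial plans an all-zero control arm; the documents do not support this, because a comparison of odds against control presupposes control events. A reader might also infer that the add-on route biases the result in favour of the label. That takes a mixture of two rules: controls scored by dish and labelled diners scored by line. Under the literal rule controls are all 0, so no bias can favour the label. Under a dish-based rule the add-on order scores 1. Under a line-based rule in both arms, bias needs more add-on use in the labelled arm, and nothing in the documents shows that. The labelled line is also close by on the same list, with a footnote explaining the label.

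What does not stand is that intent alone settles the definition. A high-salt meal could mean one of the five labelled lines, any dish above 3 g as served, or a whole order above 3 g. These can classify the same order differently, and the only written rule is none of them for a control.

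**Conclusion.** The point holds as an unreconciled outcome definition. The scoring rule and the objective depend on the label, while the analysis and the interim decision depend on the dish. As worded, the rule is wrong for the control arm and scores a dish above 3 g as 0 when it is ordered through the add-on. This assumes that plain fries with added halloumi is the dish sold on the labelled line, as the matching description and price indicate.

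The size of any bias is unknown and probably small. Odds ratios of 0.85 and 0.94 are illustrations that rest on assumed rates and on a problem confined to the labelled arm. They are not estimates of what the trial would show. Apart from scoring, one of the five labelled dishes can be ordered from a line without a label, which slightly weakens delivery of the intervention. This is a should-fix correction to the outcome definition and the menu.

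**What to change.** 1. Define the outcome identically in both arms: 1 if any dish ordered, as served and including add-ons, exceeds 3 g salt per serving by the pre-study nutritional analysis, whichever menu was seen and whichever line was used; otherwise 0.
2. Align the Secondary objectives, Experimental design, Labelled item selected, Statistical analysis (Secondary) and the interim text under Sample size to that definition and a single name.
3. Delete the chicken-or-halloumi add-on text from the fries entries on both menus. The with-chicken and with-halloumi versions already have their own lines, so no dish is lost. Rescoring alone would correct the outcome but would leave the unlabelled route open. The salad add-on text need not change, because no salad line is labelled.

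The cost is one sentence of definition, matching edits elsewhere and a small reprint of two menus. The order forms, photographs and salt analyses already planned supply everything needed.
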